5.5. Replacement of Participants

Participants may be replaced for any of the following reasons:

- In Part 1, any participant who withdraws from treatment before the completion of the DLT observation period for any reason other than a DLT (eg, not evaluable for DLT), may be replaced to ensure a minimum number of evaluable participants.
- In Part 2, participants who do not meet the eligibility requirements of the study may be replaced.

5.6. Data Monitoring Committee

This study will use an internal DMC to monitor safety and efficacy at the planned analyses. The DMC is comprised of an internal, autonomous group who are formally appointed by the sponsor. The DMC will periodically review the accumulating safety and efficacy data by treatment group, including the futility analysis, to provide advice on whether to continue, modify, or terminate a study based on a benefit-risk assessment. Additional details regarding the DMC will be provided in the DMC charter.

6. STUDY TREATMENT

6.1. Study Treatment Administered

Itacitinib IR will be self-administered in the form of 100 mg tablets.

[Table 12](#) presents the study treatment information.

Table 12: Study Treatment Information

| | Study Treatment |
|-------------------------------------|---|
| Study treatment name: | Itacitinib IR |
| Dosage formulation: | Immediate release tablets |
| Unit dose strengths: | 100 mg tablets and 300 mg tablets |
| Dose levels: | 300 mg BID and 600 mg BID |
| Route of administration: | PO |
| Administration instructions: | Itacitinib should be taken with water and regardless of food. [REDACTED] [REDACTED] |
| Packaging and labeling: | Itacitinib IR will be provided in high-density polyethylene bottles. Each bottle will be labeled as required per country requirement. Each container will be labeled as required per country requirement. |
| Storage: | Ambient conditions (15°C to 30°C, or 59°F to 86°F) |

6.2. Preparation, Handling, and Accountability

The investigator or designee must confirm appropriate temperature conditions have been maintained during transit for all study treatments received and any discrepancies are reported and resolved before use of the study treatment.

Only participants enrolled in the study may receive study treatment, and only authorized site staff may supply or administer study treatment. All study treatment must be stored in a secure, environmentally controlled, and monitored (manual or automated) area in accordance with the labeled storage conditions with access limited to the investigator and authorized site staff.

The investigator (or designee) is responsible for study treatment accountability, reconciliation, and record maintenance (ie, receipt, reconciliation, and final disposition records). Inventory and accountability records must be maintained and readily available for inspection by the study monitor and are open to inspection at any time by any applicable regulatory authorities. The investigator or designee must maintain records that document:

- Delivery of itacitinib IR to the study site.
- Inventory of itacitinib IR at the site.
- Participant use of the itacitinib IR including pill counts from each supply dispensed.
- Return of itacitinib IR to the investigator or designee by participants.

The investigational product must be used only in accordance with the Protocol. The investigator will also maintain records adequately documenting that the participants were provided the specified itacitinib IR. These records should include dates, quantities, and any available batch or serial numbers or unique code numbers assigned to the investigational product and study participants.

Completed accountability records will be archived by the site. The investigator or designee will be expected to collect and retain all used, unused, and partially used containers of itacitinib IR until verified by the study monitor (unless otherwise agreed to by the sponsor). At the conclusion of the study, the investigator or designee will oversee shipment of any remaining itacitinib IR back to the sponsor or its designee for destruction according to institutional SOPs. If local procedures mandate on-site destruction of investigational supply, the site should (where local procedures allow) maintain the investigational supply until the study monitor inspects the accountability records in order to evaluate compliance and accuracy of accountability by the investigative site. At sites where the itacitinib IR is destroyed before monitor inspection, the monitors rely on documentation of destruction per the site SOP.

Further guidance and information for the final disposition of unused study treatments are provided in the Pharmacy Manual.

Instruction to participants for handling itacitinib IR is provided in [Appendix D](#).

6.3. Measures to Minimize Bias: Randomization and Blinding

This is an open-label study; no comparisons will be made between participants or against historical controls. Measurements of safety and efficacy are objective measurements, and only comparisons to pretreatment conditions will be made.

6.4. Study Treatment Compliance

Compliance with all study-related treatments should be emphasized to the participant by the site personnel, and appropriate steps should be taken to optimize compliance during the study. Compliance with itacitinib IR will be calculated by the sponsor based on the drug accountability documented by the site staff and monitored by the sponsor/designee. Participants will be instructed to bring all unused study drugs with them to the study visits in order for site personnel to conduct tablet counts to assess study drug accountability. The drug accountability documentation will be used by the sponsor to calculate treatment compliance.

6.5. Dose-Limiting Toxicity and Determination of Recommended Phase 2 Dose

6.5.1. Definition of a Dose-Limiting Toxicity

Dose-limiting toxicity will be defined as the occurrence of any of the toxicities in [Table 13](#) (except those with a clear alternative explanation) occurring up to and including Day 28. All DLTs will be assessed for severity by the investigator with CTCAE Version 5.0. All participants who received at least 42 of 56 doses of study drug at the assigned dose level or who experienced a DLT during the first 28 days will be considered evaluable for determining tolerability of the dose.

Individual participant dose reductions may be made based on events observed at any time during treatment with study drug; however, for the purposes of dose cohort escalation/de-escalation, expanding a dose cohort, and determining the RP2D of itacitinib IR, decisions will be made based on events that are observed from the first day of study drug administration through and including Day 28.

Table 13: Definition of Dose-Limiting Toxicity

| Toxicity | Definition |
|----------------|---|
| Nonhematologic | Any \geq Grade 3 nonhematologic toxicity EXCEPT: 
• Grade 3 fatigue, asthenia, fever, anorexia, or constipation.• Grade 3 nausea, vomiting, or diarrhea not requiring tube feeding, total parental nutrition, or hospitalization/prolongation of hospitalization.• Grade 3 AST or ALT that resolves to $<$ Grade 2 within 7 days.• Grade 3 or 4 isolated electrolyte abnormalities that resolve, with or without intervention, to $<$ Grade 2 levels in $<$ 72 hours. |
| Hematologic | Any of the following: 
• Grade 3 thrombocytopenia with bleeding.• Any Grade 4 thrombocytopenia lasting $>$ 7 days.• Grade 4 decrease in neutrophil count lasting $>$ 7 days.• Grade 3 or 4 febrile neutropenia of any duration. |

6.5.2. Procedures for Cohort Review and Dose Escalation

Telephone conferences will be scheduled by the sponsor with study investigators in order to review cohort-specific safety data, adjudicate individual high grade AEs and DLTs, determine agreement with respect to dose escalation or dose elimination, and guide other major study decisions.

If 600 mg BID (Dose Level 2) is declared as the RP2D, any participants enrolled at the first dose level in Part 1 of the study will have the option of escalating to the RP2D, if they have not experienced a DLT. The participant will be required to provide consent for Part 2. Once a participant is escalated to the RP2D, the Part 2 SoA should be followed.

6.6. Dose Modifications

Selections and modifications to the study treatment regimen are planned for Part 1. Dose interruptions and modifications also may occur for individual study participants. The identification of DLTs will define the doses used in planned cohorts. Further, the occurrence of DLTs and other toxicities (related or unrelated to study drug) will guide decisions for treatment interruptions and discontinuation for individual participants.

Individual decisions regarding dose modifications of itacitinib IR should be made using clinical judgment in consultation with the medical monitor (whenever possible), taking into account relatedness of the AE to the study treatment and the participant's underlying condition. Adverse events that have a clear alternative explanation or transient (\leq 72 hours) abnormal laboratory

values without associated clinically significant signs or symptoms may be exempt from dose-reduction rules.

The decision to proceed to the next dose level (either an increase or a decrease) will be made by the study team and the investigator based on safety, tolerability, and preliminary [REDACTED] data obtained from at least 3 participants at the prior dose level.

6.6.1. Management of Dose-Limiting Toxicities or Other Urgent Situations

Investigators may employ any measures or concomitant medications necessary to optimally treat the participant after discussion with the sponsor (whenever possible).

6.6.2. Follow-Up of Dose-Limiting Toxicities

Any DLT should be monitored until it resolves to baseline or appears to have stabilized for a minimum of 2 weeks. During follow-up, participants should be seen as often as medically indicated to assure safety.

6.6.3. Criteria and Procedures for Dose Interruptions and Modifications of Study Drug

Safety concerns should be discussed with the sponsor immediately upon occurrence or awareness to determine if the participant should continue or discontinue study treatment.

Guidelines for interruption and restarting of itacitinib IR are provided in [Table 14](#).

6.6.3.1. Part 1

In Part 1, dose interruptions are permitted for individual study participants; dose modifications will not be permitted during the DLT evaluation period. The occurrence of DLTs and other toxicities (related or unrelated to study drug) will guide decisions for treatment interruptions and discontinuation for individual participants. In order to be considered evaluable in Part 1, participants must receive at least 42 of the 56 doses of study drug at the assigned dose level during the 28-day DLT evaluation period or have experienced a DLT during the first 28 days.

6.6.3.2. Part 2

Table 14: Guidelines for Interruption and Restarting of Study Drug

| Adverse Event | Action Taken |
|---|--|
| Chemistry | |
| Grade 4 increase in ALT and/or AST | 
Step 1: Interrupt study drug. Assess ALT or AST every 7 days until the toxicity has resolved to \leq Grade 1.
 
Step 2: If assessed as not related to study drug, restart study drug at same dose. If assessed as related to study drug, restart study drug at a dose 100 mg BID less than the previous dose.
 
Note: If liver tests indicate a potential Hy's Law case ($ALT > 3.0 \times ULN$, $ALP < 2 \times ULN$, and $\text{bilirubin} \geq 2.0 \times ULN$), interrupt study treatment, conduct a full work-up (including imaging if clinically indicated) to evaluate other immediately apparent possible causes of aminotransferase elevation and hyperbilirubinemia, including but not limited to, viral hepatitis, pre-existing chronic or acute liver disease, or the administration of other drug(s) known to be hepatotoxic. If Hy's Law can't be unequivocally ruled out, permanently discontinue study treatment.
 |
| Hematology | |
| Grade 4 thrombocytopenia or Grade ≥ 3 thrombocytopenia with bleeding | Interrupt dose and assess platelet count every 7 days until toxicity resolves to \leq Grade 1 or to baseline platelet count; restart study drug at 100 mg BID less than the previous dose. |
| Grade 4 thrombocytopenia and clinically significant bleeding event | Permanently discontinue study drug. |
| Grade 4 neutropenia | Interrupt dose until resolved to \leq Grade 2 or to baseline ANC. Restart dose at 100 mg BID less than the previous dose. |
| Grade 3 anemia | If hemoglobin ≥ 8.0 g/dL not achievable with transfusion of PRBC, interrupt dose until resolved \leq Grade 2. Restart dose at 100 mg BID less than the previous dose. |
| Other toxicities | |
| Any Grade 1 or Grade 2 toxicity | Continue study drug treatment and treat the toxicity; monitor as clinically indicated. |
| Any other Grade 3 toxicity | 
Step 1: Interrupt study drug. Assess relevant laboratory every 7 days until the toxicity has resolved to \leq Grade 1.
 
Step 2: If assessed as not related to study drug, restart study drug at same dose. If assessed as related to study drug, restart study drug at a dose 100 mg BID less than the previous dose.
 |

Table 14: Guidelines for Interruption and Restarting of Study Drug (Continued)

| Adverse Event | Action Taken |
|---|--|
| Other toxicities (continued) | |
| Any recurrent Grade 3 toxicity after 1 dose reduction | Interrupt study drug. Assess relevant laboratory every 7 days until the toxicity has resolved to \leq Grade 2. Restart dose at 100 mg BID less than the previous dose administration unless that lower dose is less than 200 mg BID. |
| Any other Grade 4 toxicity | Discontinue study drug administration and follow up per Protocol. When the toxicity is an isolated, unrelated, Grade 4 laboratory event that is transient and manageable with appropriate care, the investigator may choose to continue treatment at a reduced dose or after a short interruption. |

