6.6.4. Criteria for Permanent Discontinuation of Study Drug

The occurrence of unacceptable toxicity not caused by the underlying disease will require that itacitinib IR be permanently discontinued. Unacceptable toxicity is defined as follows:

- The occurrence of an AE that is related to itacitinib IR that, in the judgment of the investigator or the sponsor's medical monitor, compromises the participant's ability to continue study-specific procedures or is considered to not be in the participant's best interest.
- An AE requiring more than 2 dose reductions, if below the RP2D of itacitinib IR.
- A persistent AE requiring a delay of therapy for more than 3 weeks unless a greater delay has been approved by the sponsor.

See Section [7](#) for discontinuation procedures.

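### Table 14 directs a restart at 100 mg BID after a related Grade 4 ALT/AST rise recurs at 200 mg BID, a dose the same table bars after a recurrent Grade 3 rise

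*Combined protocol and SAP*

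**What the plan says.** The opening text of Section 6.6.3 introduces Table 14 for the drug in general: "Guidelines for interruption and restarting of itacitinib IR are provided in" that table. The table itself is printed under the Part 2 subheading. Four of its rows matter here.

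- **Grade 4 ALT/AST.** Interrupt, test weekly and wait for Grade 1 or less. An unrelated event resumes at the same dose. For a related one: "If assessed as related to study drug, restart study drug at a dose 100 mg BID less than the previous dose". The row gives no lowest dose and does not mention recurrence. Its Hy's Law note ends "If Hy's Law can't be unequivocally ruled out, permanently discontinue study treatment", but applies only when bilirubin is also at least 2.0 x ULN.
- **Any other Grade 3 toxicity.** A first Grade 3 ALT/AST rise falls here, because it has no row of its own. The recovery threshold and the reduction match the Grade 4 ALT/AST row.
- **"Any recurrent Grade 3 toxicity after 1 dose reduction".** Wait for Grade 2 or less, then go down a further 100 mg BID, "unless that lower dose is less than 200 mg BID".
- **Any other Grade 4 toxicity.** "Discontinue study drug administration and follow up per Protocol", with an exception for isolated, unrelated, transient laboratory events.

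Section 6.6.4 requires a permanent stop for "An AE requiring more than 2 dose reductions, if below the RP2D of itacitinib IR". It also requires one when a persistent event holds up treatment for more than 3 weeks, unless the sponsor agrees to longer.

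**The concern.** Elsewhere the protocol treats Grade 4 as the worse liver event. Table 13 spares one kind of Grade 3 rise from counting as a DLT ("Grade 3 AST or ALT that resolves to" below Grade 2 within 7 days) and spares no Grade 4 ALT/AST rise. A related Grade 4 toxicity without its own row in Table 14 ends treatment. Yet after two related Grade 4 ALT/AST rises the written rule is to re-expose the participant, at a dose the table does not allow after two Grade 3 rises.

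At stake is a third exposure after two related Grade 4 liver events. Scheduled chemistry in the extension period is every 8 weeks (Table 4, Section 8.6), and Table 14 adds no closer ALT/AST checks once dosing resumes. All 4 treated participants received 300 mg BID, the starting dose at which the gap opens, and those still on treatment continue until they meet withdrawal criteria (Section 4.1).

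**Working it through.** The protocol states no figure to reproduce. The check traces the dose steps and then asks whether another rule blocks them.

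**Inputs.** Starting dose 300 mg BID (Section 4.1); step 100 mg BID and floor 200 mg BID (Table 14); stop at more than 2 reductions (Section 6.6.4); tablets of 100 mg and 300 mg (Table 12), so 100 mg BID can be dispensed.

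**Dose paths for related events**

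| Event | First event | Recurrence at 200 mg BID |
|---|---|---|
| Grade 3 ALT/AST | 300 − 100 = 200 | 200 − 100 = 100, below 200: barred |
| Grade 4 ALT/AST | 300 − 100 = 200 | 200 − 100 = 100: restart |
| Grade 4 toxicity with no row of its own | Stop | Not reached |

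The Grade 4 ALT/AST path uses 2 reductions, which is not more than 2, so that limit in Section 6.6.4 does not block it. From 600 mg BID, two reductions give 600 → 500 → 400, which stays above the floor, so the conflict does not arise there. The documents report no participant treated at 600 mg BID.

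**What the floor means.** The recurrent Grade 3 row does not say what to do when the lower dose is barred.

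- If it means stop: Grade 3 has 1 restart (200 mg BID) and Grade 4 has 2 (200, then 100 mg BID).
- If it means stay at 200 mg BID: Grade 3 has 2 restarts (200, 200) and Grade 4 has 2 (200, 100).

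On both readings 100 mg BID is open to Grade 4 and closed to Grade 3. The extra restart appears only on the first.

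**Hy's Law rules.** The note in Table 14 needs raised bilirubin. Appendix E is wider, because the elevations need not coincide and ALP is ignored, but it also needs raised bilirubin. When its criteria are not met, it refers the investigator back to Section 6.6.3. An isolated Grade 4 ALT/AST rise therefore returns to the same row.

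**Reach.** The documents give no rate of Grade 4 ALT/AST rises. Assume a probability *p* of 1% to 5% per participant for a first related event, and *q* of 10% to 50% for recurrence after one reduction. The chance that at least one of 4 reaches the 100 mg BID step is 1 − (1 − *pq*)⁴:

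- *p* = 0.01, *q* = 0.10: 1 − 0.999⁴ = 0.4%
- *p* = 0.01, *q* = 0.50, or *p* = 0.05, *q* = 0.10: 1 − 0.995⁴ = 2.0%
- *p* = 0.05, *q* = 0.50: 1 − 0.975⁴ = 9.6%

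Using all 4 is an upper bound, because the number still on treatment is not stated.

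**The case against.** The best defence has four parts.

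1. **The Grade 4 path is stricter on recovery.** On recurrence, a Grade 4 rise must fall to Grade 1 or less, against Grade 2 or less for Grade 3. With the 3-week delay limit in Section 6.6.4, this can decide whether a restart happens at all, not only when. This stands. It narrows the path, but a participant who recovers in time is still directed to 100 mg BID.
2. **These are guidelines.** Section 6.6 leaves individual dose changes to clinical judgment in consultation with the medical monitor, Section 6.6.3 calls for immediate discussion with the sponsor, and Section 6.6.4 lets the investigator or monitor stop the drug. This also stands and lowers the priority. It does not make the written default sound.
3. **200 mg BID is not a minimum for the whole table.** The Grade 4 neutropenia row, and the row for Grade 4 thrombocytopenia without clinically significant bleeding, also restart 100 mg BID lower with no floor. A reader might infer that Table 14 stops every other related Grade 4 toxicity. It does not; that holds only for Grade 4 events without a row of their own.
4. **Reach is minimal.** Enrollment is closed, Part 2 will not run, and Table 14 is printed under Part 2. Applying it to ongoing Part 1 participants relies on the Section 6.6.3 lead-in and the Appendix E referral. Dose changes are barred during the DLT window, so the gap matters only after Day 28.

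A reader might also argue from Table 7 that 100 mg BID is too weak to justify re-exposure. That does not carry the point. JAK2 inhibition measures activity, not liver safety, and 200 mg BID already misses the stated targets (15.3 average and 47.0 maximal, against 20% to 30% and 50% to 70%), yet the table permits it.

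**Conclusion.** The gap is real but narrow. As written, Table 14 directs a restart at 100 mg BID after a related, isolated Grade 4 ALT/AST rise recurs at 200 mg BID, while barring that dose after a recurrent Grade 3 rise. No other written dose, reduction or Hy's Law rule closes the path for a participant who recovers within the permitted delay.

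A reader might go further and call the table inverted, with two restarts for Grade 4 against one for Grade 3. The text does not settle that. It follows only if the floor means stop; if it means stay at 200 mg BID, the restarts are equal in number and the Grade 4 participant ends on the lower dose.

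The size is at most 4 participants, and 0.4% to 9.6% for the chance that any of them reaches the step. That range rests wholly on assumed event rates. Minor priority.

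**What to change.** Add one sentence to the Grade 4 ALT/AST row of Table 14:

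> If a related Grade 4 ALT/AST rise recurs after 1 dose reduction and the next lower dose would be below 200 mg BID, permanently discontinue study drug; do not restart at the dose at which it recurred.

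The last clause is needed. A bare floor could be read as allowing re-challenge at 200 mg BID, where the event has just recurred, and that is more exposure than the present rule gives. The sentence reuses the 200 mg BID threshold but adds an explicit stop, which the recurrent Grade 3 row does not have. The hematology rows and Section 6.6.4 can stay as they are.

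The cost is one sentence and no added assessments. The downside is that a participant who might have tolerated 100 mg BID loses that option.

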6.6.4. Criteria for Permanent Discontinuation of Study Drug

The occurrence of unacceptable toxicity not caused by the underlying disease will require that itacitinib IR be permanently discontinued. Unacceptable toxicity is defined as follows:

- The occurrence of an AE that is related to itacitinib IR that, in the judgment of the investigator or the sponsor's medical monitor, compromises the participant's ability to continue study-specific procedures or is considered to not be in the participant's best interest.
- An AE requiring more than 2 dose reductions, if below the RP2D of itacitinib IR.
- A persistent AE requiring a delay of therapy for more than 3 weeks unless a greater delay has been approved by the sponsor.

See Section [7](#) for discontinuation procedures.

6.6.5. Permitted Medications and Procedures

Concomitant treatments and/or procedures that are required to manage a participant's medical condition during the study will also be recorded in the eCRF.

All concomitant medications and treatments (including over-the-counter or prescription medicines, vitamins, vaccines, and/or herbal supplements) must be recorded in the eCRF. Any prior medication received up to 30 days before the first dose of study treatment and 30 days after the last dose of study treatment will be recorded in the eCRF. Any addition, deletion, or change in the dose of these medications will also be recorded. Concomitant medications administered up to 30 days after the last dose of study treatment for an SAE should be recorded for SAEs as defined in Section [9.4](#).

